	
To remove the sensitivity analyses for the primary efficacy endpoint.
 
Minor discrepancy corrected.
	
-Section 6.4 and 6.4.1: updated to include moderate potency topical corticosteroids and systemic corticosteroids.
 
-Section 9.3.1: Removed the following sentence: Moreover, the analyses performed on observed case (i.e. without imputation of missing observations) will be done as sensitivity analyses.
 
- Synopsis and Section 5.1: Added the abbreviation ‘e.g’ to inclusion criterion #7.

6.0 / 01 October 2019	
To update a sponsor contact.
 
To remove the upper limit of age as requested by the FDA, as CHE occurs in patients >75 years of age.
 
To allow recruitment of up to 30 additional subjects, because of the high dropout rate observed in the study. This will ensure the statistical power of the primary analysis is maintained by having at least 75 subjects completing the 16 weeks of treatment.
 
To correct the number of study centers participating in this study.
	
- Title Page: Updated the name of sponsor’s associate director – clinical operations, to reflect that [name] occupies this position for now on.
 
- Synopsis, Section 4.1, and Section 5.1 (Inclusion Criterion #1): Updated to include subjects aged 18 years or older in the study.
 
- Synopsis and Section 4.1: Updated to allow inclusion of approximately 105 subjects in the study.
 
- Section 1.2 (study diagram): Updated the number of subjects to 35 for each group.
 
- Synopsis and Section 9.1: Added the following sentence to the sample size considerations: Assuming between 25-30% dropout rates, up to 35 patients per group will be included in this study.
 
- Synopsis and Section 4.1: Updated the number of study centers participating in this study from 15-20 to 20-25.

STATEMENT OF COMPLIANCE

The trial will be conducted in accordance with the protocol, International Council for Harmonisation (ICH) Good Clinical Practice (GCP), and applicable local regulations. The principal investigator will assure that no planned deviation from, or changes to the protocol will take place without prior agreement from the sponsor and documented approval from the institutional review board (IRB), except where necessary to eliminate an immediate hazard(s) to the trial subjects. All personnel involved in the conduct of this study have completed ICH GCP training.

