
Actual PaGA measurements at Weeks 4, 8, 12, 16, 32Change from baseline in hand Dermatology Life Quality Index (DLQI) at Weeks 2, 4, 8, 12, 16, and 32Change and percent change from baseline in pain visual analog scale (VAS) at Weeks 4, 8, 12, 16, and 32		
Secondary safety endpoints include: 
Number of treatment-emergent adverse events (TEAEs)Number of drug-related TEAEsProportion of subjects withdrawing for worsening of their CHE at Weeks 4, 8, 12, and 16Changes in vital signs, electrocardiogram (ECG), and safety laboratory tests		
Secondary pharmacokinetic (PK) endpoint includes: 
Measurement of plasma concentrations of ASN002 in all subjects receiving ASN002 treatment		
Exploratory Endpoints: Exploratory endpoints include: 
Change from baseline in PD, biomarkers and skin microbiome analysis at Weeks 4 and 16Characterization of population PK parameters via nonlinear mixed-effects modelingEvaluate clinical safety, efficacy and biomarker measurements in relationship to PK exposureChange and percent change from baseline in Extent of Disease affected with moderate to severe CHE at Weeks 4, 8, 12, 16, and 32Change from baseline Work Productivity and Activity Impairment – Specific Health Problem (WPAI-SHP) questionnaire for hands at Weeks 4, 8, 12, 16, and 32Change and percent change from baseline in foot mTLSS at Weeks 4, 8, 12, 16, and 32Proportion of subjects achieving at least a 2-grade reduction from baseline to clear (0), almost clear (1) or mild (2) in foot PGA at Weeks 4, 8, 12, 16, and 32Proportion of subjects achieving a foot PGA of clear (0) or almost clear (1) at Weeks 4, 8, 12, 16 and 32Change and percent change from baseline in foot PGA at Weeks 4, 8, 12, 16, and 32Change and percent change from baseline in Extent of Disease affected with foot eczema at Weeks 4, 8, 12, 16, and 32		
Study Design: This study will be performed at approximately 20-25 study centers located in the United States and Canada.		

Name of Sponsor/Company: Asana BioSciences, LLC	Name of Investigational Product: ASN002	Name of Active Ingredient: ASN002

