9.3.3 Safety Analyses

All safety data, including AEs and SAEs will be presented and tabulated according to MedDRA classification. Descriptions of AEs will include the start date, the stop date (if it resolved), the severity and seriousness of the AE, the causality of the AE to study product, and the outcome. The focus in this protocol will be the prevalence of treatment-emergent adverse events (TEAEs).

Reported AEs will be summarized by the number of subjects reporting the events, as well as by System Organ Class, Preferred Term, severity, seriousness, and relationship to study product. For the summary of AEs by severity, each subject will be counted only once within a System Organ Class or a Preferred Term by using the AEs with the highest intensity within each category for each analysis. For the summary of AEs by relationship to study product, each subject will be counted only once within a System Organ Class or a Preferred Term by using the AEs with the greatest reported relationship within each category. For the summary of AEs by relationship to study product and severity, each subject will be counted only once within a System Organ Class or a Preferred Term by using (1) the greatest reported relationship followed by (2) the highest reported intensity.

All information pertaining to AEs noted during the study will be listed by subject, detailing verbatim, System Organ Class, Preferred Term, start date, stop date, intensity, outcome, and relationship to study product. The AE onset will also be shown relative (in number of days) to the day of study product administration. Serious adverse events will be tabulated by treatment group, relationship to the test article, and a reference to the occurrence of the SAEs to the relative day of dosing.

Results from laboratory analyses, vital signs, and ECGs will be tabulated by treatment and visit using descriptive statistics. The value at each visit as well as the change from baseline will be presented descriptively.

Concomitant medications will be coded with the World Health Organization Drug Dictionary (WHO-DD) and listed by subject. Summary of medication classes will also be tabulated.

No inferential statistics will be done on safety variables.

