2 STUDY OBJECTIVES AND ENDPOINTS

OBJECTIVES	ENDPOINTS
Primary	Efficacy endpoint:
To evaluate the efficacy of ASN002 in subjects with moderate to severe chronic hand eczema (CHE) based on hand modified Total Lesion Symptom Score (mTLSS)	
 Percent change from baseline in hand mTLSS at Week 16
Secondary	Efficacy endpoints:
To evaluate the efficacy of ASN002 in subjects with moderate to severe CHE.	
 Change from baseline in hand mTLSS at Weeks 4, 8, 12, 16 Percent change from baseline in hand mTLSS at Weeks 4, 8, and 12 Proportion of subjects achieving at least a 2-grade reduction from baseline to clear (0), almost clear (1) or mild (2) in hand PGA at Weeks 4, 8, 12 and 16 Proportion of subjects achieving a hand PGA of clear (0) or almost clear (1) at Weeks 4, 8, 12 and 16 Change from baseline in hand PGA at Weeks 4, 8, 12 and 16

PPD	STATISTICAL ANALYSIS PLAN, Version Final 1.0
Protocol Number: ASN002AD-202 V6.0	Sponsor: Asana BioSciences, LLC

OBJECTIVES	ENDPOINTS
	
 • Change and percent change from baseline in Hand Eczema Severity Index (HECSI) at Weeks 4, 8, 12 and 16 • Time to response relative to baseline (based on hand PGA) • Actual hand Patient Global Assessment (PaGA) at Weeks 4, 8, 12 and 16 • Change from baseline in hand Dermatology Life Quality Index (DLQI) at Weeks 2, 4, 8, 12 and 16 • Change and percent change from baseline in pain visual analog scale (VAS) at Weeks 4, 8, 12 and 16
	Safety endpoints:
To evaluate the safety and tolerability of ASN002 in subjects with moderate to severe CHE	
 • Number of Treatment Emergent Adverse Events (TEAEs) • Number of drug-related TEAEs • Proportion of subjects withdrawing for worsening of their CHE at Weeks 4, 8, 12, and 16 • Changes from baseline in vital signs • Change from baseline in ECG • Change from baseline in safety laboratory tests
	Pharmacokinetic endpoints:
To quantify the plasma concentrations of ASN002 in subjects with moderate to severe CHE	
 • Measurement of plasma concentrations of ASN002 in all subjects receiving ASN002 treatment.
Exploratory	Exploratory endpoints:
To evaluate pharmacodynamic (PD), biomarkers and skin microbiome analysis for evidence of drug activity in subjects with moderate to severe CHE	
 • Change from baseline in PD, biomarkers and skin microbiome analysis at Weeks 4 and 16.

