11 STUDY TREATMENT EXPOSURE AND TREATMENT COMPLIANCE

A summary of exposure will be presented using the safety population for each treatment group and will include descriptive statistics of the number of days treated for each treatment group. For each treatment, compliance will be calculated as follow:

$$\frac{\text{Number of doses taken}}{\text{Number of days between the last dose date and the first dose date} + 1} \times 100$$

Descriptive statistics for compliance will be presented for each treatment group. Frequency distribution will also be presented for the following categories: < 80%, [80% - 120%] and > 120%.

Exposure and compliance will be displayed in a listing of study treatment administration.

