14.1 Adverse Events

Adverse events (AEs) will be coded according to the Medical Dictionary for Regulatory Activities (MedDRA), Version 21.0.

Treatment emergent adverse event (TEAE) is any condition that was not present prior to treatment with the study product but appeared following first dose in Part A, was present at treatment initiation but worsened during treatment, or was present at treatment initiation but resolved and then reappeared while the individual was on treatment (regardless of the intensity of the AE when the treatment was initiated). See [Appendix 2](#) for handling of completely or partially missing dates for AEs. In the case where it is not possible to define an AE as treatment emergent or not, the AE will be classified as treatment emergent. AEs will be considered in Part A or Part B depending on the onset date – if the AE onset date was on or before week 16 the AE will be considered as a Part A AE. If the AE had an onset after week 16 the AE will be considered as a Part B AE. AEs emerged in part A and last into part B would be reported in both parts A and B and be noted in the part B report for these AEs which are reported twice.

An overall summary table of adverse events will be provided. The number of events and the number and percentage of subjects who experienced AE, TEAE, TEAE by greatest reported relationship, TEAE by relationship, TEAE by highest reported severity, TEAE by severity, related TEAE by highest reported severity, related TEAE by severity, serious AE, serious TEAE, serious TEAE by greatest relationship, TEAE and related TEAE leading to study drug discontinuation, TEAE and related TEAE leading to study discontinuation, TEAE and related TEAE leading to treatment interruption and AE leading to death will be presented as well as TEAE of clinical interest.

TEAE of clinical interest are:

- Thrombotic events

PPD	STATISTICAL ANALYSIS PLAN, Version Final 1.0
Protocol Number: ASN002AD-202 V6.0	Sponsor: Asana BioSciences, LLC

- Serious infection
- Malignancy and lymphoproliferative disorders
- Gastrointestinal perforation
- Hypersensitivity
- Anemia
- Neutropenia
- Lymphopenia
- Liver enzyme elevation
- CPK and lipid elevation

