Unless otherwise specified, a subject experiencing the same TEAE multiple times will be counted only once for the corresponding PT. Similarly, if a subject experiences multiple TEAEs within the same SOC, the subject will be counted only once for that SOC. TEAEs will be sorted alphabetically by SOC and within each SOC the PT will be presented by decreasing order.

Frequency and percentage of subjects who experience TEAE will be summarized by SOC and PT within SOC.

Frequency and percentage of subjects who experience TEAE will be summarized by SOC, PT, and relationship. A treatment-related TEAE is defined as any TEAE that is assessed by the investigator as probably or possibly related to study treatment. TEAE that is assessed as not related will be defined as not treatment-related. If a subject experiences more than one TEAE within different relationship categories within the same SOC/PT, only the worst case (greatest reported relationship) will be reported. A TEAE with an unknown relationship will be considered as treatment-related.

Frequency and percentage of subjects who experience TEAE will be summarized by SOC, PT, and severity (mild/moderate/severe). If a subject experiences more than one TEAE within different severity categories within the same SOC/PT, only the worst case (highest reported severity) will be reported. TEAE with an unknown severity will be considered as severe.

Frequency and percentage of subjects with TEAEs will be summarized by SOC, PT, relationship, and severity (mild/moderate/severe). Each subject will be counted only once within a System

PPD	STATISTICAL ANALYSIS PLAN, Version Final 1.0
Protocol Number: ASN002AD-202 V6.0	Sponsor: Asana BioSciences, LLC

Organ Class or a Preferred Term by using (1) the greatest reported relationship followed by (2) the highest reported intensity. TEAE with an unknown severity will be considered as severe.

Frequency and percentage of subjects who experience serious TEAE will be summarized by SOC and PT within SOC.

Frequency and percentage of subjects who experience serious TEAE will be summarized by SOC, PT, and relationship. If a subject experiences more than one serious TEAE within different relationship categories within the same SOC/PT, only the worst case (greatest reported relationship) will be reported.

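### Part A adverse events are summarised without any allowance for time at risk, so uneven dropout between arms could distort both event counts and crude percentages

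*Protocol*

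**What the plan says.** The endpoint lists give a count with no unit, denominator or time basis: "Number of treatment-emergent adverse events (TEAEs" in the protocol synopsis and "Number of Treatment Emergent Adverse Events (TEAEs" in SAP 2. The number of drug-related TEAEs is listed in the same way.

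The analysis text goes further:

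- Protocol 9.3.3: "Reported AEs will be summarized by the number of subjects reporting the events". The same section rules out inferential statistics on safety.
- SAP 14.1, overall table: "The number of events and the number and percentage of subjects who experienced AE, TEAE", and further categories.
- SAP 14.1, detailed tables: "Frequency and percentage of subjects who experience TEAE will be summarized by SOC and PT within SOC". Relationship and severity tables follow the same pattern.
- SAP Appendix 1: the default percentage denominator is the population size in each treatment group.

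SAP 11 will give "descriptive statistics of the number of days treated for each treatment group", and SAP 7.1 summarises days in study. Neither is linked to adverse events. No patient-time rate or time-to-first-event summary of adverse events appears in either document.

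On dropout, the version 6.0 entry in the protocol history adds up to 30 subjects "because of the high dropout rate observed in the study". Protocol 9.1 and SAP 5.1 assume 25-30% and give no figure by arm.

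**The concern.** Part A is the only placebo-controlled period, so its descriptive adverse-event tables carry the whole safety comparison with placebo. A subject who leaves at Week 4 has a quarter of the planned time in which to report an event, yet counts fully in the denominator.

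The protocol gives reasons why exits might differ by arm. Under 6.4.3, starting a prohibited topical CHE treatment in the first 8 weeks leads to discontinuation of study product and an early termination visit. Section 7.1 lists the need for another effective therapy as a reason for discontinuation. If ASN002 works as assumed in 9.1, these exits may fall more on placebo. The laboratory and event criteria in 4.4.2 may fall more on ASN002. Section 8.7.5 does not record worsening CHE as an adverse event, so a subject who leaves for worsening loses time at risk and the reason for leaving adds no event. Withdrawal for worsening is itself a listed safety endpoint.

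The net direction is unknown. Earlier exit on placebo would make ASN002 look more harmful than it is, and earlier exit on ASN002 would make it look safer.

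**Working it through.** **Inputs from the documents.** Part A lasts 16 weeks, allocation is 1:1:1 with up to 35 per group, and overall dropout is 25-30%.

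**The plan's own figure.** No figure is given for the TEAE endpoint. The dropout allowance reproduces closely: 25/0.75 = 33.3 and 25/0.70 = 35.7, against 35 stated.

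**Assumptions.** Dropout *d* by arm, even timing of exits over 16 weeks, a constant event rate that is equal in both arms, and a first-event hazard of 4 per 100 subject-weeks. Placebo at 40% with both active arms at 20% would average (40 + 20 + 20)/3 = 26.7%, inside the planned range. The reverse pattern averages (20 + 40 + 40)/3 = 33.3%, slightly above it.

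**Step 1: event counts.** Mean time at risk is 16 × (1 − d/2). With equal rates and arm sizes, the count ratio equals the ratio of these times.

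- 40% dropout: 16 × 0.80 = 12.8 weeks
- 20% dropout: 16 × 0.90 = 14.4 weeks
- Ratio 14.4/12.8 = 1.125, or 12.5% more events in the lower-dropout arm. Seen from the other arm, 12.8/14.4 = 0.889, or 11% fewer.

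**Step 2: crude percentages.** Incidence among completers is 1 − exp(−0.04 × 16) = 1 − exp(−0.64) = 47.27%. For leavers, averaged over even exit times, it is 1 − 0.4727/0.64 = 26.14%.

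- 40% dropout: 0.6 × 47.27 + 0.4 × 26.14 = 38.8%
- 20% dropout: 0.8 × 47.27 + 0.2 × 26.14 = 43.0%

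**Step 3: range.**

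| Dropout, higher vs lower arm | Mean weeks at risk | Count ratio, lower/higher | Crude incidence |
|---|---|---|---|
| 40% vs 20% | 12.8 vs 14.4 | 1.125 | 38.8% vs 43.0% |
| 30% vs 25% | 13.6 vs 14.0 | 1.03 | 40.9% vs 42.0% |
| 27.5% vs 27.5% | 13.8 vs 13.8 | 1.00 | 41.5% vs 41.5% |

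Timing matters too. If all leavers go at Week 4, mean time is 16(1 − d) + 4d. At 30% vs 25% this is 12.4 vs 13.0 weeks, a ratio of 1.05.

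**Step 4: what a rate would show.** Expected time to first event or exit is incidence divided by hazard. For 35 subjects at 40% dropout, 35 × 0.388 = 13.6 first events over 13.6/0.04 = 340 subject-weeks. At 20% dropout, 35 × 0.430 = 15.1 first events over 15.1/0.04 = 376 subject-weeks. Both give 4.0 per 100 subject-weeks, which is the assumed truth.

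**The case against.** A reader might infer that the safety analysis is only a raw count and that the arms therefore cannot be compared. The documents do not support that. SAP 14.1 pairs counts with subject percentages, and the detailed tables are by subject. Single arms are planned equal. The pooled ASN002 Overall column in Part A would show about twice the placebo count at equal rates and dropout (70/35), but the percentage beside it does not depend on column size. With similar dropout, the percentages remain comparable.

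Four further objections have weight:

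- **Size.** The 40% vs 20% split is assumed. Even there, 43.0 − 38.8 = 4.2 points is about 1.5 subjects in 35, against a standard error of the difference of about 11.7 points. At 30% vs 25% it is under half a subject.
- **Visibility.** Days treated, disposition by part, reasons for discontinuation and withdrawals for worsening are all tabulated, so a reader could see an exposure imbalance. They could not convert it into rates for each event category.
- **Constant hazard.** Protocol 2.1.2 reports that the commonest Phase 1b event was headache, mostly on Day 1. Later dropout does not affect the percentage for such an event. Dividing its count by 12.8 and 14.4 weeks would make the lower-dropout arm look 11% better with no true difference. Rates should therefore not replace the percentages.
- **Time at risk.** Days treated in SAP 11 are not split by part and do not give time to first event. In SAP 14.1, the first limb of the TEAE definition has no end-of-treatment limit, so counted events can fall outside treated days.

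These points limit the concern and shape the remedy. They do not remove the gap.

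**Conclusion.** The gap is real and modest. Part A TEAEs are reported only as counts and crude percentages, with no allowance for time at risk, in a trial that enlarged enrolment because of dropout. If exits differ by arm, both displays may be distorted, in a direction that cannot be foreseen. The count bias runs from zero at equal dropout, through about 3% at 30% vs 25%, to 12.5% at 40% vs 20%, where crude incidence is about 39% vs 43%. These sizes rest on assumed dropout by arm, exits spread evenly over 16 weeks, and a constant, equal event rate; the incidences also rest on the assumed hazard. No planned test is invalidated, since safety is descriptive. A supplementary rate, fixed before unblinding, would let readers separate an exposure difference from a difference in event rate.

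**What to change.** In SAP 14.1:

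1. Define the endpoint's main display as subjects with at least one TEAE (n, %), and likewise for drug-related TEAEs. Label event counts as descriptive.
2. For Part A, add two supplementary columns: events per 100 subject-weeks, and subjects with a first event per 100 subject-weeks to first event or end of Part A observation. Apply them to TEAEs, related TEAEs, serious TEAEs and TEAEs of clinical interest.
3. Define time at risk to match the Part A counting window: first dose to the Week 16 visit or, for subjects who leave earlier, last Part A contact.
4. State that the rates assume a roughly constant hazard and are read beside the percentages, with particular care for events that cluster early.

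The cost is SAP wording, one extra derivation and longer adverse-event tables. No new data are needed and trial conduct does not change.

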1.2 Study Diagram

Figure 1: Study Diagram

1.3 Schedule of Events

The screening evaluation will only be performed after the subject has agreed to participate and has signed and dated the informed consent form. No treatment or trial-related procedures will be initiated before the informed consent is signed. The Day 1 visit must be performed, at the latest, 30 days after the screening visit. The screening evaluation will be performed according to the inclusion and exclusion criteria. If the subject fulfills all inclusion criteria and no exclusion criteria, he or she may be included in the study.

Table 1 provides a description of the procedures to be performed at each visit.

Unless specified otherwise, the study assessments scheduled during the study visits will be performed before the study product administration. If assessments are scheduled for the same nominal time, then the assessments should occur in the following order:

- Patient reported outcomes and PaGA
- Vital signs
- 12-lead ECG
- Blood draw for PK evaluations (time window vs drug administration detailed in footer of Table 1) and/or safety blood draw

Note: The timing of the assessments should allow the blood draw to occur within the allowed window of the nominal time.

Table 1. Schedule of Events

Study Visits	Screening	Treatment Period											Follow-up / ET
		Part A						Part B					
Day (D); Week (W)		D1	W2 (D15)	W4 (D29)	W8 (D57)	W12 (D85)	W16 (D113)	W18 (D127)	W20 (D141)	W24 (D169)	W28 (D197)	W32 (D225) EOT ^a	
Window (days)	-30 to -1		±1	±1	±2	±2	±2	±2	±2	±2	±2	±2	±2
Informed consent	X												
Demographics	X												
Medical and surgical history	X	X											
Patch testing history	X	X											
Inclusion-exclusion criteria	X	X											
Pregnancy test ^b	X	X	X	X	X	X	X	X	X	X	X	X	X
Physical examination	X	X			X ^c		X			X ^c		X	X ^c
Vital signs ^d	X	X	X	X	X	X	X	X	X	X	X	X	X
ECG ^e	X	X		X	X		X		X	X		X	X ^f
Clinical laboratory tests (hematology, chemistry, and urinalysis)	X	X		X	X	X	X		X	X	X	X	X
Serology (HIV, HBV, HCV)	X												
Tuberculosis evaluation ^g	X												
BSA (excluding hands and feet) (subjects with AD only)	X	X											
vIGA (excluding hands and feet) (subjects with AD only)		X		X			X						
Diagnostic Criteria for Atopic Dermatitis (subjects with AD only)	X												
Presence or absence of foot eczema	X	X											
Extent of Disease ^h		X	X	X	X	X	X		X	X	X	X	X
HECSI		X	X	X	X	X	X		X	X	X	X	X
mTLSS ^h		X	X	X	X	X	X		X	X	X	X	X
PGA ^h	X	X	X	X	X	X	X		X	X	X	X	X
PaGA		X	X	X	X	X	X		X	X	X	X	X
DLQI		X	X	X	X	X	X		X	X	X	X	X

Study Visits	Screening	Treatment Period											Follow-up / ET
		Part A						Part B					
Day (D); Week (W)		D1	W2 (D15)	W4 (D29)	W8 (D57)	W12 (D85)	W16 (D113)	W18 (D127)	W20 (D141)	W24 (D169)	W28 (D197)	W32 (D225) EOT ^a	W36 (D253) EOS
Window (days)	-30 to -1		±1	±1	±2	±2	±2	±2	±2	±2	±2	±2	±2
WPAI-SHP		X	X	X	X	X	X		X	X	X	X	X
Pain Visual Analog Scale		X	X	X	X	X	X		X	X	X	X	X
Skin microbiome analysis [worst hand (palmar aspect, when possible) involved with eczema (and plantar aspect (when possible) of foot, if foot involvement)] ⁱ		X		X			X						X ^j
Tape strips collection [from hand (and foot if applicable)] ^k		X		X			X						X ^j
Skin biopsies collection ^l		X		X ^m			X						X ^j
Blood sampling for PD analyses ⁿ		X		X ^m			X						X ^j
Blood sampling for PK evaluation		X ^o	X ^p	X ^o	X ^p	X ^p	X ^p		X ^p	X ^p	X ^p	X ^p	X ^{f,p}
Randomization		X											
Study product administration at study center		X	X	X	X	X	X		X	X	X	X	
Study product administration daily ^q		X-----											
Emollient use on hands and feet (if foot eczema) ^r		X-----											X
Dispensing of study product		X		X	X	X	X ^s		X	X	X		
Study product collection/accountability/compliance ^t			X ^u	X	X	X	X		X	X	X	X	X ^f
Photograph of both aspects (palmar and dorsal) of both hands ^v		X			X		X			X		X	X
Concomitant medication	X	X	X	X	X	X	X	X	X	X	X	X	X
Adverse events evaluation	X	X	X	X	X	X	X	X	X	X	X	X	X

BSA=Body Surface Area; DLQI=Dermatology Life Quality Index; ECG=electrocardiogram; EOS=end of study; EOT=end of treatment; ET=early termination; HBV=hepatitis B virus; HCV=hepatitis C virus; HECSI=hand eczema severity index; HIV=human immunodeficiency virus; mTLSS=modified Total Lesion

Study Visits	Screening	Treatment Period											Follow-up / ET
		Part A						Part B					
Day (D); Week (W)		D1	W2 (D15)	W4 (D29)	W8 (D57)	W12 (D85)	W16 (D113)	W18 (D127)	W20 (D141)	W24 (D169)	W28 (D197)	W32 (D225) EOT ^a	W36 (D253) EOS
Window (days)	-30 to -1		±1	±1	±2	±2	±2	±2	±2	±2	±2	±2	±2

Symptom Score; PaGA=Patient Global Assessment; PD=pharmacodynamic; PGA=Physician's Global Assessment; PK=pharmacokinetics; VAS=visual analog scale; WPAI-SHP=Work Productivity and Activity Impairment – Specific Health Problem.

^a The end of treatment (EOT) visit will occur on the first day of Week 32 (D 225) (+/- 2 days).

^b Females of childbearing potential only. Serum pregnancy test at screening and urine pregnancy test at other visits.

^c Brief physical examinations.

^d Including height, weight and BMI. Height will be measured only at screening and the same value will be used for BMI calculation at other visits.

^e ECG will be recorded at 0 (pre-dose, within 1 hour prior to dosing), 1 (\pm 30 min), and 3 (\pm 1 hour) hours post-dose on Day 1, Week 4, Week 16 and Week 20. ECG will be recorded only once at screening, Weeks 8, 24 and 32 and ET visit (if applicable).

^f Only at ET

^g If PPD is used, a second screening visit will be necessary.

^h mTLSS, Extent of Disease and PGA to be assessed only for hands and feet, but evaluated separately.

ⁱ Microbiome samples will be collected for all subjects prior to tape stripping collection and skin biopsy (if applicable). Microbiome samples will be collected on Day 1, Week 4 and Week 16 (or ET visit, if applicable) (one from lesional skin (palmar aspect (when possible) of the worst hand) and one from adjacent nonlesional skin). At each visits samples should be collected from the same areas selected on Day 1. Microbiome samples should be collected prior to study product administration and after photographs, if applicable. If the subject has presence of foot eczema on Day 1, microbiome samples (lesional and non lesional) will be collected from the plantar aspect (when possible) of the worst foot.

^j Only at ET, if ET visit is performed prior to Week 16.

^k Skin tape stripping samples will be collected for all subjects as close as possible to the site of microbiome collection (preferably the same palmar lesion when possible) and of the skin biopsy (if applicable). Skin tape stripping samples will be collected on Day 1 (one from lesional skin and one from adjacent nonlesional skin) and one at Week 4 and Week 16 (or ET visit, if applicable) (from same lesional area as Day 1). Tape stripping should be collected prior to study product administration and after photographs, if applicable. If the subject has presence of foot eczema on Day 1, skin tape stripping samples will also be collected from the foot (one from lesional skin and one from adjacent nonlesional skin) at Day 1 and one at Week 4 and Week 16 (or ET visit, if applicable) from same lesional skin as Day 1.

^l Optional, only for a subset of approximately 36 subjects who consent: two 2.5-mm skin biopsies at Day 1 (one from lesional skin and one from adjacent nonlesional skin) and one at Week 16 (or ET visit, if applicable) (from the same lesional skin as Day 1) and preferably from the same lesion as the one selected for the microbiome and tape stripping sampling. Biopsies are collected from the palmar aspect of the hand and should be collected adjacent to the tape stripping site. Subjects consenting to biopsies collection must also consent to PD samples. Biopsies should be collected prior to study product administration and after photographs, if applicable.

^m An additional skin biopsy from same lesional skin as Day 1 (and adjacent from the tape stripping site) and PD sample will be collected at Week 4 for subjects who consent to four biopsies.

ⁿ Optional, only for a subset of approximately 36 subjects who consent: PD samples to be drawn as trough samples prior to study product administration. Subjects consenting to PD samples must also consent to biopsies. PD samples should be collected prior to study product administration.

Study Visits	Screening	Treatment Period											Follow-up / ET
		Part A						Part B					
Day (D); Week (W)		D1	W2 (D15)	W4 (D29)	W8 (D57)	W12 (D85)	W16 (D113)	W18 (D127)	W20 (D141)	W24 (D169)	W28 (D197)	W32 (D225) EOT ^a	W36 (D253) EOS
Window (days)	-30 to -1		±1	±1	±2	±2	±2	±2	±2	±2	±2	±2	±2

^o PK samples will be collected at 0 (pre-dose), 2 (± 30 min) hours post-dose and 6 hours post-dose (between 5 to 12 hours post-dose). The dosing time for the previous day should be recorded accurately.

^p PK samples will be collected at 0 (pre-dose) and 2 (± 30 min) hours post-dose. The dosing time for the previous day should be recorded accurately. At ET visit (if applicable), only one PK sample will be collected.

^q Study products will be taken at home daily for 32 weeks, except on study visit days when the study products will be administered on site. For visit Week 18, subjects will dose at home.

^r Emollient use must be initiated at least 1 week prior to Day 1.

^s On this visit, subject who were receiving placebo since Day 1, will start receive ASN002 80 mg until EOT visit.

^t Subject should be instructed to always bring their medication to the site when there is a scheduled visit.

^u On Week 2 visit, there will be no collection/dispensing, but subject will dose on site with the medication kit dispensed on Day 1.

^v Optional, only for a subset of approximately 36 subjects who consent. Photographs should be performed prior to drug administration, biopsy (if applicable) and tape stripping and microbiome sample collection.

